All things considered, the thorough examination of the exclusions, withdrawals, and reported adverse effects in the pooled analysis sheds light on the difficulties and conclusions that have been found in a number of research. It emphasizes how crucial it is to closely monitor participant outcomes and unfavorable occurrences in clinical research in order to guarantee the efficacy and safety of the medicines being studied(30).

The treatment for distal ureteral stones with size less than 10 mm with tamsulosin and silodosin has resulted in a high output rates of 57-64% and 80 - 84%, respectively, according to randomized controlled studies. Nonetheless, compared to other trials, the tamsulosin success rate in those investigations is somewhat lower (31). However, tamsulosin demonstrated an 86% success rate in a randomized controlled study with almost 3000 patients(32). Tamsulosin has a 67–90.7% success rate in treating distal ureteral stones, according to Tao

et al.'s meta-analysis.20 The current study's tamsulosin success rates align with some studies (33).

Similar to the current investigation, the comparable rates in the Imperatore et al. study were 82% and 88%, and in the Arda et al. study they were 72.4% and 78.6%. These investigations also revealed no discernible difference between tamsulosin and silodosin. However, only young/middle-aged men were included in this study, whereas both of other investigations included both men and women. This sums up the main distinction between prior studies and the present investigation (34).

Tamsulosin is used commonly in our population for MET however Silodosin, a newer drug, is not used frequently for this purpose and is still under research. Also, comparison of Silodosin and Tamsulosin has not been explored in our population earlier.

Rationale

The purpose of this study is to examine and compare the effectiveness of silodosin and tamsulosin in medical expulsive therapy (MET) in terms of the rate at which stones are expelled from the body, as well as the adverse effect profiles in our patient group.

OBJECTIVES:

To evaluate and compare the efficacy and safety of medical expulsive therapy containing tamsulosin and silodosin, specifically.

To compare the side effect profile of tamsulosin and silodosin when given for medical expulsive therapy.

HYPOTHESIS:

Null Hypothesis:

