It is hypothesized that efficacy and safety of medical expulsive therapy, containing tamsulosin and silodosin, is almost the same and silodosin can be used with the same efficacy for the treatment of lower urinary tract calculi.

Alternative Hypothesis:

Silodosin is better than Tamsulosin in efficacy and safety.

OPERATIONAL DEFINITIONS:

STONE CLEARANCE:

Stone clearance will be defined as no evidence of stone on follow up X-ray KUB imaging at 4 weeks .

ANCILLARY PROCEDURES:

Additional urological procedures needed to remove the same stone for which medical expulsive therapy was given if it fails to remove the stone completely.

SIDE EFFECTS:

Any undesirable effect noticed after prescription of the drug including but not limited to abnormal ejaculation, headache, orthostatic hypotension, backache and gastritis etc.

MATERIALS AND METHODS:

STUDY DESIGN:

Prospective randomized control trial.

STUDY SETTING:

Outpatient department of Sir Ganga Ram hospital, Lahore.

DURATION OF STUDY:

18 months.

DURATION OF TREATMENT:

Four weeks.

SAMPLE SIZE:

Using the open-epic software, the sample size was estimated. The minimum sample size that we require is 208 patients with ureteric stone who fulfil the inclusion criterion with 104 in one group receiving tamsulosin and 104 in silodosin group (1:1 ratio) with an inflation of 10 percent for estimated loss to follow up, with an anticipated expulsion rate ranging from 58-64 percent in tamsulosin group and 78-83 percent in silodosin group with a risk difference of 19 to achieve a power of 80 percent and a level of significance of 5 percent.

SAMPLING TECHNIQUE:

Patients visiting the outpatient department of Sir Ganga Ram hospital will be selected by simple random sampling, fulfilling the inclusion criteria.

SAMPLE SELECTION:

Adult male and female patients fulfilling the inclusion criteria will be assigned into two groups by random allotment, 1^{st} group will be given Tamsulosin and 2^{nd} group will be given Silodosin for four weeks.

INCLUSION CRITERIA:

Following factors make up the inclusion criteria for this study.

- Patients between ages 18 years 55 years.
- Solitary unilateral ureteral stone
- Stone sizes less than 10 mm measured on non-contrast computed tomography of kidney, ureter and bladder.
- Stones being treated primarily with medical expulsive therapy
- Radio opaque Stone

EXCLUSION CRITERIA:

The presence of following factors will exclude the patients from our study:

- Pregnancy
- Untreated UTI

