Data will be entered and analyzed on SPSS version 22. Percentages and frequencies will be calculated for the demographic variables of the patients. The comparison of the two groups will be made by using T- test. P-value of less than 0.05 will be considered significant and the power used will be 0.80.

RESULTS

Frequency and percentage of demographic data

Variables		Frequency	Percentage	
Gender	Male	105	58.7	
	Female	74	41.3	
Income	Less than	108	60.3	
status	50000			
	50000 -150000	69	38.5	
	Greater than	2	1.1	
	150000			
	Normal	166	92.7	
BMI	Obese	13	7.3	
	None	136	76.0	
Comorbidity	HTN	33	18.4	
	Diabetes	10	5.6	

This information sheds light on the sample population's health and demographic distribution, showing a preponderance of people with normal BMIs and lower income levels, as well as a significant percentage of people without comorbid diseases.

In our study there are total 179 patients out of which 74 are females (41.3%) and 105 males (58.7%).

The income, 108 people, or 60.3% of the total, make less than 50,000Rs in month. Just 2 members, or 1.1 percent, make more than 150,000 monthly, while 69 participants (38.5%) have monthly salaries between 50,000 and 150,000.

13 persons (7.3%) are classed as obese, while 166 people (92.7%) have a normal BMI. These numbers represent a sizable fraction of the sample. In terms of comorbidities, 136 individuals (76.0%) state they have no comorbid conditions. Of the people with comorbidities, 10 (5.6%) had diabetes, and 33 (18.4%) had hypertension (HTN).

[figure not shown]

Figure 1: Pie chart of patients using Silodosin and Tamsulosin (Medicine Advised)

Use of medicine (Figure 1)

Tamsulosin and Silodosin, the two drugs prescribed to a group of patients, are distributed as shown in the pie chart. Of the patients, 43% were advised to take Tamsulosin, which is shown as the blue section on the chart. And (57%) of the patients were advised to take silodosin, as shown by the red segment.

Table2: Patient demographic characteristics and study variables are

Varibales	Tamsulosin	Silodosin	p-value	
Body Mass index	Normal	72(43.4%)	94(56.6%)	0.730
	obese	5 (38.5%)	08(61.5%)	
Laterality	Right	65(55.6%)	52(44.4%)	0.001
	Left	12(19.4%)	50(80.6%)	
Symp To CT	Less than 1 week	67(64.4%)	37(35.6%)	
	More than 1 week	10(15.2%)	56(84.8%)	0.001
	More than 2 week	0 (0.0%)	09(100%)	
Posl n Ureler	Proximal	28(51.9%)	26(48.1%)	

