	Mid	08(17.4%)	38(82.6%)	0.001
	Distal	41(51.9%)	38(48.1%)	
Water intake	Less than 1 litre	59(54.6%)	49(45.4%)	
	More than 1 litre	18(25.4%)	53(74.6%)	0.001
Analgesic requirement	Yes	26(61.9%)	16(38.1%)	0.005
	No	51(37.2%)	86(62.8%)	
Time for removal	Less than 14 days	6(10.3%)	52(89.7%)	
	14-21	14(27.5%)	37(72.5%)	0.001
	22-28	57(81.4%)	13(18.6%)	

presented as frequency and percentage with association

The table compares several factors along with the corresponding p-values to assess statistical significance between two drugs tamsulosin and silodosin.

First, based on Body Mass Index (BMI), 43.4% of those with a normal BMI were prescribed Tamsulosin, while 56.6% were recommended Silodosin. On the other hand, among those who were obese, 38.5% were given Tamsulosin and 61.5% were given Silodosin; p-value came out to be 0.730, which meant that there was no statistically significant variation in the medication preferences according to BMI.

15.2% of patients who had pain for more than a week prior to CT scan, received Tamsulosin while 84.8% received silodosin.

51.9% of the patients with proximal ureteric stone were given Tamsulosin and 48.1% received Silodosin.

82.6 percent of patients with mid-ureteric stone problems received Silodosin, while 17.4% received Tamsulosin.

51.9% of patients with distal ureteric stones received Tamsulosin and 48.1% on Silodosin.

Only 38.1% of patients on Silodosin required analgesics, whereas 61.9% of patients on Tamsulosin used analgesics.

89.7% of patients on silodosin had their stone removed in less than 14 days, while only 10.3% of the patients on Tamsulosin had their stone removed in aforementioned duration.

72.5% of patients on Silodosin had their stone removed in 14-21 days, while only 27.5% of the patients on Tamsulosin had their stone removed in same duration.

Moreover, 81.4% on Tamsulosin had their stone removed in 22-28 days and 18.6% patients on Silodosin had it removed in same duration.

		Tamsulosin	Silodosin	p- value
Side	None	61 (40.1%)	91(59.9%)	
effect	Othostatic	09 (60.0%)	06(40.0%)	
	hypotension			0.3.15
	Abnormal	2(66.7%)	1(33.3%)	
	ejaculation			
	Headache	5(55.6%)	4 (44.4%)	

Table 2 Association between Tamsulosin and Silodosin with side effects

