The side effects that patients using silodosin and tamsulosin experienced are analyzed in the table, and the p-value denotes the statistical significance of these data. Patients on Silodosin, with no side effects were 59.9% while 40.1% on Tamsulosin did not report any side effects. This implies that, in comparison to Tamsulosin, Silodosin may have a marginally higher correlation with patients reporting no adverse effects.

Examining particular side effects reveals various themes. Nine patients on tamsulosin (60.0%) and six patients on silodosin (40.0%) developed orthostatic hypotension, a condition marked by a considerable drop in blood pressure upon

standing. It suggested that Tamsulosin users are more likely to have orthostatic hypotension than Silodosin users.

Only a very tiny percentage of patients reported abnormal ejaculation; 2 individuals on tamsulosin (66.7%) and 1 patient on silodosin (33.3%). Again, this points to an increased chance of this specific adverse effect in Tamsulosin users.

[figure not shown]
Another side effect that was identified involved headaches, which were seen by 4 individuals on silodosin (44.4%) and 5 patients on tamsulosin (55.6%). Headaches were marginally more common among Tamsulosin users compared to Silodosin users, similar to orthostatic hypotension.

None of the detected differences in side effect distribution between Tamsulosin and Silodosin is statistically significant, according to the p-value of 0.315. This implies that even if there are discernible variations in the frequency of particular adverse effects between the two drugs, these variations might just be the result of random variation rather than an actual distinction in the side effect profiles of tamsulosin and silodosin.

In conclusion, the analysis of side effects reveals that patients taking silodosin have a tendency to report no side effects more often than individuals taking tamsulosin. On the other hand, it seems that tamsulosin users are more likely to experience certain adverse effects, like headache, orthostatic hypotension, and abnormal ejaculation. Even with these findings, the absence of statistical significance suggests that more investigation using larger sample sizes would be necessary to conclusively identify any significant variations in the side effect profiles of Tamsulosin and Silodosin.

Figure 2

Bar Chart showing comparison of stone expulsion rate in Tamsulosin and

Silodosin groups

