Similar results were seen in another study showing that, individuals receiving just tamsulosin treatment needed a greater average analgesic dosage of 391.43 \pm 165.60 mg with a p-value of 0.005, which denotes substantial significance, the necessary(50).

Similarly, a study showed statistically significant difference in the amount of analgesics needed by patients treated with Silodosin compared to those treated with tamsulosin only. The robustness of the conclusion was highlighted by the fact that the group receiving Silodosin treatment required considerably fewer analgesics than the groups receiving Tamsulosin, with a p-value of < 0.001(51).

Conclusion

An effective treatment for ureteral stones is medical expulsive therapy. According to our findings, silodosin has a safer profile and is more successful than tamsulosin at ejecting ureteric stones.

Silodosin had an increased rate of stone expulsion and took less time in stone expulsion compared to those treated with Tamsulosin.

In addition, patients treated with silodosin reported fewer side effects, such as a retrograde ejaculation, orthostatic hypotension and headaches as compared to those taking Tamsulosin.

In addition, those who received Silodosin needed less analgesic medication than those who received Tamsulosin.

•

REFERENCES

- Ahmed AFAM, Al-Sayed AYS. Tamsulosin versus Alfuzosin in the Treatment of Patients with Distal Ureteral Stones: Prospective, Randomized, Comparative Study. Korean J Urol. 2010 Mar;51(3):193–7.
- 5. Pietropaolo A, Proietti S, Geraghty R, Skolarikos A, Papatsoris A, Liatsikos E, et al. Trends of 'urolithiasis: interventions, simulation, and

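### The side-effect table gives no rates by arm, and one 3-df p-value is used to judge every effect, so the safety conclusion has no estimate behind it

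*Combined protocol and SAP*

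**What the plan says.** The Objectives include a safety aim: "To compare the side effect profile of tamsulosin and silodosin when given for medical expulsive therapy". The Hypothesis section gives it a direction: "Silodosin is better than Tamsulosin in efficacy and safety". The Operational Definitions leave the list of side effects open: "Any undesirable effect noticed after prescription of the drug including but not limited to abnormal ejaculation, headache, orthostatic hypotension, backache and gastritis etc".

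The Data Analysis Procedure names one method for comparing the arms: "The comparison of the two groups will be made by using T- test". It names no method for categorical or safety data, and no safety endpoint.

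The Results give one table, titled "Association between Tamsulosin and Silodosin with side effects". It has four rows, with percentages that add to 100% across each row, and one p-value. The text applies that p-value to every effect: "None of the detected differences in side effect distribution between Tamsulosin and Silodosin is statistically significant, according to the p-value of 0.315". The Conclusion nevertheless states that "patients treated with silodosin reported fewer side effects, such as a retrograde ejaculation, orthostatic hypotension and headaches" compared with tamsulosin, and the Abstract claims a better safety profile for silodosin.

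**The concern.** Three things go wrong together.

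- **One p-value for every effect.** A 3-df test asks whether the mix of four labels differs by drug. It gives no direction, estimate or interval. It is not a test of hypotension, headache or ejaculation taken singly, nor of the proportion of patients with any side effect.
- **Row shares read as patient rates.** A row share depends on arm size as well as risk. The arms are unequal (77 and 102), so a drug with identical risk would still hold 102/179 = 57.0% of every row if it were silodosin. The printed 59.9% must be judged against that figure, not against 50%.
- **No arm-level result.** A directional safety hypothesis needs a rate per arm and a difference with its uncertainty. Neither is reported.

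Safety is one of the trial's stated aims and part of its headline conclusion. As reported, the Results say the differences may be chance and the Conclusion says silodosin is safer. The reader is given no estimate with which to choose between them.

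**Working it through.** **Inputs** (side-effect table in the Results)

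| | Tamsulosin | Silodosin | Total |
|---|---|---|---|
| None | 61 | 91 | 152 |
| Orthostatic hypotension | 9 | 6 | 15 |
| Abnormal ejaculation | 2 | 1 | 3 |
| Headache | 5 | 4 | 9 |
| Sum | 77 | 102 | 179 |

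The sums match the BMI rows of the characteristics table (72 + 5 = 77; 94 + 8 = 102) and the 179 patients reported as analysed. Two-sided tests are assumed, because the plan does not state sidedness.

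**1. Reproducing the reported p-value.** Expected count = row total × arm total / 179. Pearson chi-square = Σ(O − E)²/E:

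0.294 + 0.222 + 1.006 + 0.759 + 0.390 + 0.295 + 0.329 + 0.248 = 3.54 on 3 df, p = 0.315.

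This matches the report. Three of the eight expected counts are below 5: 3 × 77/179 = 1.29, 3 × 102/179 = 1.71 and 9 × 77/179 = 3.87. The Fisher-Freeman-Halton exact test gives p = 0.32, so sparseness does not change the answer. A t-test on the category codes, the nearest thing to the planned method, gives p = 0.129.

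**2. Row shares against arm rates for no side effect.**

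- Row shares, as printed: 61/152 = 40.1%; 91/152 = 59.9%.
- Arm rates: 61/77 = 79.2%; 91/102 = 89.2%.

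**3. Any side effect.**

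- Tamsulosin: 9 + 2 + 5 = 16; 16/77 = 20.8%.
- Silodosin: 6 + 1 + 4 = 11; 11/102 = 10.8%.
- Difference: 10.0 points.
- Wilson limits: 13.2% to 31.1% (tamsulosin) and 6.1% to 18.3% (silodosin).
- Newcombe lower limit: 0.0999 − √[(0.2078 − 0.1322)² + (0.1829 − 0.1078)²] = −0.007.
- Newcombe upper limit: 0.0999 + √[(0.3112 − 0.2078)² + (0.1078 − 0.0613)²] = 0.213.
- Chi-square: 179 × (16 × 91 − 11 × 61)² / (77 × 102 × 27 × 152) = 3.42 on 1 df, p = 0.064. Fisher p = 0.090; with Yates correction p = 0.101.

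About 3.42/3.54 = 97% of the 3-df statistic is therefore the any-versus-none contrast. The other two degrees of freedom add only about 0.12.

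**4. Single effects, all patients as denominator.**

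| Effect | Tamsulosin | Silodosin | Fisher p |
|---|---|---|---|
| Orthostatic hypotension | 9/77 (11.7%) | 6/102 (5.9%) | 0.18 |
| Headache | 5/77 (6.5%) | 4/102 (3.9%) | 0.50 |
| Abnormal ejaculation | 2/77 (2.6%) | 1/102 (1.0%) | 0.58 |

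The ejaculation rates should use men only. There are 105 men overall, with no split by arm. If both arms had the overall 58.7% male share (an assumption), there would be about 45 and 60 men, giving 2/45 = 4.4% and 1/60 = 1.7%.

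**5. Sensitivity to arm size.** The Abstract gives 89 and 93 patients, which add to 182 rather than its stated 180. Putting the same event counts over those sizes gives 16/89 = 18.0% v 11/93 = 11.8%, Fisher p = 0.30.

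**The case against.** The strongest reply is that the sentence on non-significance is true. Every single effect, and any effect, stays above 0.05 after re-analysis, and the exact version of the omnibus test agrees with the reported one. The Results also say that larger samples are needed. All of that stands.

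Four stronger readings are tempting, and the documents do not support them.

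- **That patients were forced into one category.** The rows sum exactly to each arm, so each patient appears to hold one label, but no coding rule is stated. The sums also fit a trial in which no patient had two effects. Under independence, the expected overlap of hypotension and headache is only 15 × 9/179 = 0.75 patients.
- **That the any-effect comparison was hidden.** The counts without side effects are printed, and the Results remark on the tendency in words. The Discussion even describes the 40.1% and 59.9% correctly, as shares of those without side effects. What is missing is arm rates, a difference and an interval.
- **That the test has no bearing on the objective.** The objective is to compare profiles, and an omnibus test is a crude global comparison of profiles. It falls short on direction, size and single effects.
- **That 0.064 in place of 0.315 shows silodosin is safer.** The any-effect contrast was chosen after the data were seen, no safety endpoint was planned, and the interval includes zero.

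One further caution stands. The arms differ at baseline: right-sided stones 65/77 (84.4%) v 52/102 (51.0%), mid-ureteric stones 8/77 (10.4%) v 38/102 (37.3%), and symptoms for under a week before CT 67/77 (87.0%) v 37/102 (36.3%). Even a clear difference in side effects could not simply be put down to the drug.

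**Conclusion.** The point holds as a fault of analysis and reporting in a stated objective. One omnibus p-value is made to speak for each effect, row shares are presented as patient rates (59.9% where the arm rate is 89.2%), and no arm-level estimate is given for a directional safety hypothesis.

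The best summary of the printed data is a difference of 10.0 points in any side effect, favouring silodosin, with a 95% CI from 0.7 points the other way to 21.3 points. That is compatible with no difference and with a substantial one: a possible reduction, not established. A reader might infer either that the drugs have the same side-effect profile or that silodosin is safer. The data show neither, and the Abstract and Conclusion go further than the Results allow.

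This rests on the table's own arm sizes of 77 and 102, on each affected patient being counted once, and on two-sided testing. If patients with two effects were entered in two rows, the any-effect counts would change. If the Abstract's arm sizes were right, the difference would shrink to about 6.2 points (18.0% − 11.8%).

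**What to change.** 1. Replace the row percentages with n/N and percentages by arm, and correct the sentences that read row shares as patient rates.
2. Add any side effect as the overall safety comparison, labelled post hoc: 16/77 (20.8%) v 11/102 (10.8%), risk difference 10.0 points, 95% CI -0.7 to 21.3, Fisher p = 0.090.
3. Report each effect descriptively, with arm rates and Fisher's exact test. Use men only as the denominator for abnormal ejaculation. Stop applying 0.315 to single effects.
4. Reword the Abstract and Conclusion from a safer profile to a possible reduction that was not established, and mention the baseline imbalances.
5. Reconcile the Abstract's 89 and 93 with the 77 and 102 in the tables before finalising any rate.
6. State the coding rule. Where source records allow, tabulate each effect as a separate yes/no item, including backache and gastritis, which the definition names but the table does not show.

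Steps 1 to 4 need only re-tabulation and rewording, with no new data, apart from a split of men by arm, which should be in the dataset. Step 5 needs the patient-level allocation and follow-up records. Step 6 may not be fully achievable: if only one label per patient was recorded, multiple effects cannot be recovered, and the report should say so.

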This bar chart presents a comparative examination of the rates of stone expulsion for patients who were suggested to take Tamsulosin or Silodosin during three distinct time periods—less than 14 days, 14–21 days, and 21–28 days.

The results are color-coded, with red bars denoting silodosin and blue bars denoting tamsulosin.

Silodosin shows a markedly greater efficacy in stone expulsion, with about 55 patients expulsing stone in less than 14 days in comparison to just about 5 patients on Tamsulosin.

This suggests that Silodosin is far more successful at facilitating stone removal in less time than Tamsulosin.

While in 14–21days duration, Silodosin continues to work better than Tamsulosin in removing stones. About 20 patients on Tamsulosin were able to successfully remove stone, compared to about 30 people on Silodosin. This implies that while tamsulosin is also beneficial, silodosin retains greater efficacy.

In the span of 21–28 days, 57 patients on Tamsulosin while 13 on Silodosin were able to eliminate stones. In general, Silodosin is quite successful for rapid stone ejection during the first two weeks. Using the intended period for stone

ejection to guide medicine selection, this time-dependent efficacy analysis offers clinicians important information.

[figure not shown]

Figure 3 Survival function

This statistical method is commonly used to estimate the time until an event occurs and to compare the survival curves of different groups. In this case, Kaplan–Meier analysis was performed to assess the duration that patients required to expel kidney stones while receiving either silodosin or tamsulosin treatment. The rate of the expulsion of stone and the time for it, for both groups, was evaluated using this method, as can be seen in Figure 2.

The log-rank test was applied to compare the rate and time for stone expulsion between the two groups. It is a hypothesis test for comparing the survival distributions of two samples. It was used in this study to see if patients treated with silodosin and those treated with tamsulosin had significantly different times for stones to be expelled. With a p-value of 0.05, the log-rank test findings showed that there was statistically significant difference between the two groups. This indicates that both groups' times to stone expulsion were statistically comparable.

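### Expulsion counts per time band, given without arm denominators or numbers still at risk, cannot support choosing the drug by intended expulsion period

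*Combined protocol and SAP*

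**What the plan says.** The Figure 2 text in Results presents the bar chart as a comparison of expulsion rates over three periods (under 14, 14–21 and 21–28 days), but it gives only numbers of patients:

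- First band, silodosin first: "about 55 patients expulsing stone in less than 14 days in comparison to just about 5 patients on Tamsulosin".
- Second band: "About 20 patients on Tamsulosin were able to successfully remove stone, compared to about 30 people on Silodosin".
- Last band: "57 patients on Tamsulosin while 13 on Silodosin were able to eliminate stones".

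It reads the first two bands as efficacy in favour of silodosin. For the last band it states the counts without comment. It then says that, taking the intended period of stone "ejection to guide medicine selection, this time-dependent efficacy analysis offers clinicians important information".

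The underlying counts are in the first of the two tables labelled Table 2 (patient characteristics and study variables), in the time-for-removal rows. The text below that table reads its percentages as patient rates, for example: "Moreover, 81.4% on Tamsulosin had their stone removed in 22-28 days and 18.6% patients on Silodosin had it removed in same duration". The Discussion repeats these percentages as a main result.

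**The concern.** Each band is treated as a separate efficacy comparison. After the first band that is not valid. Patients who have already expelled cannot expel again, so the number available to expel in a later band depends on what happened earlier. A slow arm has more stones left and will show a larger late count even if the drug does nothing special late on. Raw counts are also not comparable between arms of different size, even in the first band.

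What is at stake is the closing sentence. It offers clinicians a basis for drug choice by intended period, and the data shown do not support any period-specific choice. The percentages add to the problem. They are shares of all patients in a band across both arms, but they are worded as the proportion of an arm that expelled.

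**Working it through.** **Inputs.** Time-for-removal counts from the first Table 2, tamsulosin v silodosin: under 14 days 6 v 52; 14–21 days 14 v 37; 22–28 days 57 v 13. Analysed total: "In our study there are total 179 patients". Arm share: "43% were advised to take Tamsulosin".

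**Arm totals.** 6 + 14 + 57 = 77 and 52 + 37 + 13 = 102. Then 77 + 102 = 179 and 77/179 = 43.0%, which agrees with the stated total and share. The three bands therefore contain every analysed patient.

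**Reproducing the printed percentages.** Formula: count ÷ (both arms' counts in that band).

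- Under 14 days: 6/58 = 10.3%, 52/58 = 89.7%.
- 14–21 days: 14/51 = 27.5%, 37/51 = 72.5%.
- 22–28 days: 57/70 = 81.4%, 13/70 = 18.6%.

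All six match the table, so the denominator is the band, neither the arm nor the patients still holding a stone.

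**Arm-based percentages, number at risk and cumulative expulsion.** At risk = arm total minus earlier expulsions. Cumulative = expulsions so far ÷ arm total.

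| Band | Arm | At risk at start | Expelled in band ÷ at risk | Expelled in band ÷ arm | Cumulative |
|---|---|---|---|---|---|
| <14 d | T | 77 | 6/77 = 7.8% | 7.8% | 7.8% |
| <14 d | S | 102 | 52/102 = 51.0% | 51.0% | 51.0% |
| 14–21 d | T | 77 − 6 = 71 | 14/71 = 19.7% | 14/77 = 18.2% | 20/77 = 26.0% |
| 14–21 d | S | 102 − 52 = 50 | 37/50 = 74.0% | 37/102 = 36.3% | 89/102 = 87.3% |
| 22–28 d | T | 71 − 14 = 57 | not estimable | 57/77 = 74.0% (as printed) | not estimable |
| 22–28 d | S | 50 − 37 = 13 | not estimable | 13/102 = 12.7% (as printed) | not estimable |

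**Why the last band is not estimable.** The at-risk numbers, 57 and 13, equal the band counts by construction, because the bands hold all 179 patients. The resulting 57/57 and 13/13 are forced and say nothing about either drug. They also imply 100% expulsion in both arms by four weeks, against the 58–64% (tamsulosin) and 78–83% (silodosin) anticipated in the sample-size section. If the last row includes patients whose stone had not passed, the true late rates could lie anywhere from 0 to 100% in either arm. For illustration, 10 tamsulosin non-expellers would give 47/57 = 82.5%, and 3 silodosin non-expellers would give 10/13 = 76.9%.

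**Check under a stated assumption.** Keep all 104 randomised per arm at risk and count patients missing from the table as not expelled. The last band then becomes 57/(104 − 20) = 57/84 = 67.9% v 13/(104 − 89) = 13/15 = 86.7% (Fisher p about 0.22). The 57 v 13 gap gives no tamsulosin advantage here either.

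**The case against.** **A late tamsulosin advantage is the reader's inference.** Someone could take 57 v 13, the 81.4% figure and the advice to choose by period as meaning that tamsulosin is the better drug in week four. The report does not say this. It draws no efficacy comparison for the last band, credits silodosin in the first two, and favours silodosin in the Abstract and Conclusion. This objection stands, and the point is limited to the unsupported period-based advice.

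**The opposite inference fails too.** A reader might conclude from 57/57 and 13/13 that the drugs are equally effective late on. Those fractions are forced by the layout of the table, so they are no evidence of equality.

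**Patients at risk are handled elsewhere.** Kaplan–Meier and log-rank analyses follow directly, and in principle they account for who still has a stone. Figure 3 is not in the text available, so it cannot be said whether it shows numbers at risk. This stands in part: the fault lies in the Figure 2 text and the table, not in every analysis. But the band-by-band advice does not draw on those analyses. Their text points to Figure 2, which is captioned as the bar chart, and describes the log-rank result as significant, as comparable and as not significant. That is a separate defect, but it means the reader is given no clear at-risk result with which to correct the counts.

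**Little changes.** After correction silodosin is still ahead at days 14 and 21. No sample size or overall conclusion moves. This stands, and it lowers the severity.

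**Conclusion.** The period-based advice is wrong as written; severity is moderate. Counts per band, from arms of 77 and 102 and without numbers at risk, do not measure efficacy within a period. The late 57 v 13 mainly shows how many were left: 74.0% of the tamsulosin arm and 12.7% of the silodosin arm had not expelled by day 21. What the table can support is cumulative expulsion of 7.8% v 51.0% at day 14 and 26.0% v 87.3% at day 21 (tamsulosin v silodosin).

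This rests on three assumptions: that the first Table 2 is the correct source, that 77 and 102 are the right denominators, and that the first two bands contain only true expulsions. The Figure 2 text gives slightly different approximate counts for those bands (about 5 and 20 for tamsulosin, about 55 and 30 for silodosin), but the picture is the same. No late-band rate, and no late ordering of the drugs, can be recovered from what is printed.

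**What to change.** 1. Delete the sentence on medicine selection and make no period-specific efficacy claim from band counts.
2. Replace the counts in the Figure 2 text with the number at risk and the cumulative proportion expelled per arm, with 95% CIs: day 14, 6/77 (7.8%) v 52/102 (51.0%); day 21, 20/77 (26.0%) v 89/102 (87.3%). Make the figure text agree with the table, including the last-band label (21–28 v 22–28 days).
3. Give day 28 only after confirming which last-band patients had not cleared on the four-week X-ray, and list them separately. Otherwise the report would print 100% in both arms unchecked.
4. State the denominators used and reconcile the three sets: 104/104 randomised, 89/93 in the Abstract (which sum to 182, against the 180 stated there), and 77/102 in the table.
5. In the text under the first Table 2 and in the Discussion, replace the row percentages with arm-based ones: before day 14, silodosin v tamsulosin, 51.0% v 7.8% in place of 89.7% v 10.3%; 14–21 days, silodosin v tamsulosin, 36.3% v 18.2% in place of 72.5% v 27.5%; last band, tamsulosin v silodosin, 74.0% v 12.7% in place of 81.4% v 18.6%, subject to item 3.
6. Say how the day of expulsion was established, since the only scheduled imaging described is at four weeks.

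Items 1, 2 and 5 cost a few lines of text and one small table from counts already held. Items 3, 4 and 6 need a check of the follow-up records and the participant flow, but no new data collection.
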